### **20.1 Introduction**

The Chair's Office is responsible for the overall scientific and administrative conduct of the TRTT, along with the coordination and management of the project. All technical questions with regard to treatment and complications shall be directed to the Chair's Office. In addition, preparations for meetings shall also be arranged through the Chair's Office. The Study Chair's office also has responsibility for recruiting, organizing, and managing the Clinical Centers and subcontracting for services in the Clinical Centers.

### **20.2 Responsibilities**

The Chair's Office is responsible for the overall scientific and administrative conduct of the trial. Specific duties include:

- Planning, developing, and refining the TRTT design, including cooperation with the Director of the Data Coordinating Center (DCC) in preparing the Manual of Procedures and necessary institutional review board protocols for the Chair's Office, Coordinating Center, and Clinical Centers;
- Developing the placebo sound generator (SG) and process for coordination of production and delivery of conventional and placebo SGs;
- Recruiting, organizing, and supervising all Clinical Centers;
- Developing and maintaining a three-party contract, including the University of Alabama (UA), Johns Hopkins University (JHU), and each clinical site as the parties. Cooperative Research and Development Agreements (CRADAs) have been prepared by the UA legal office in conjunction with Naval and Air Force officials and reviewed and signed by UA, JHU, and each clinical site.
- Organizing training sessions for Study Audiologists to learn the principles, theory, and practice of TRT and consensus standard of care (SC) across the military Clinical Centers;
- Resolving all technical questions with regard to treatment and complications;
- Making meeting arrangements for the Steering Committee (STC), Executive Committee (EC), and the Full Investigative Group (FIG);
- Preparing and distributing meeting minutes to the appropriate committee members;
- Preparing the training videotapes for directive counseling (DC), SC, and SG fitting;
- Coordinating publicity on a local and national level to enhance patient recruitment;
- Monitoring target enrollment and recruitment of minorities and women at each Clinical Center in collaboration with the DCC;
- Monitoring adherence to protocol at each Clinical Center through regular communication, evaluation of voice recorded counseling sessions, and site visits at each Clinical Center;
- Assisting with preparation and assembly of reports;

- Developing scientific publications and presentations in conjunction with the Coordinating Center and other TRTT investigators;
- Preparing continuation grant proposals with other TRTT investigators; and
- Supervising closeout of each TRTT Clinical Center at the end of the study.

## **20.3 Organization**

### **20.3.1 Introduction**

The Chair's Office is located on the Campus of the University of Alabama within the Department of Communicative Disorders.

### **20.3.2 Personnel and Their Responsibilities**

#### **20.3.2.1 Study Chair**

The Study Chair is responsible for the overall scientific and administrative conduct of the trial. He is responsible for:

- Ensuring that the objectives of the project are met.
- Maintaining Institutional Review Board compliance, budgeting and accounting of Military Clinical Centers via a sub-contractual arrangement;
- Training, coordination and oversight of the Study Audiologists who will provide the assigned treatments at the Clinical Centers; and
- Supervision of personnel and consultants in the Study Chair's Office.

He shall serve as Chair of the EC and the STC, as a voting member of the Quality Assurance Committee (QAC), and the FIG. He will also serve as a non-voting member of the Data and Safety Monitoring Committee (DSMB). He will correspond regularly and be in close contact with the chairs of all standing committees and will appoint new committees as the occasion arises during the conduct of the study. The Study Chair will participate in the protocol monitoring visits to all Clinical Centers and his office has responsibility for general oversight of each Clinical Center and their clinical activities as part of the TRTT. All issues including study design, eligibility, exclusion criteria, therapeutic considerations, etc. shall be addressed by the Study Chair. He also has primary responsibility, along with the Director of the DCC in publishing and presenting the findings of the TRTT.

### **20.3.2.2 Training/Protocol Monitor**

The Training/Protocol Monitors are responsible for the training programs and for monitoring adherence to the directive counseling (DC) and standard-of-care (SC) protocols. One Training/Protocol Monitor will have expertise with DC, and a second Training/Protocol Monitor will have expertise with SC. Both will have responsibility for relevant training and quality control. The former Training/Protocol Monitor will be responsible for instructing Study Audiologists in the fitting of sound therapy (ST) devices and follow-up care. The study responsibilities for the Training/Protocol Monitors include:

- Training and certifying Study Audiologists to provide the TRTT treatments;
- Working with the Study Chairman in preparing the DC, SC, and sound generator (SG) fitting training videotapes;
- Talking and corresponding with the Study Otolaryngologists and Audiologists regarding study protocol, especially with respect to clinical measures and DC and SC;
- Participating in site visits and monitoring for adherence to protocol at the Clinical Centers; and
- Monitoring adherence to DC and SC protocols by reviewing voice recordings of TRTT treatment sessions.

### **20.3.2.3 Study Otolaryngologist**

The roles of this physician, who has experience in participating as a member of a clinical team providing TRT, are to:

- Train Clinical Center Study Otolaryngologists in medical evaluation of tinnitus patients and determination of eligibility;
- Assist the Study Chair's Office in medically related matters pertaining to patient eligibility for the TRTT and treatment-related complications; and
- Serve as a general medical resource to Study Otolaryngologists.

#### **20.3.2.4 Administrative Assistant/Meeting Coordinator**

The Administrative Assistant/Meeting Coordinator assists the Study Chair in all aspects of the study. This individual shall have the following specific duties and responsibilities:

- Attending all technical group meetings and preparing minutes of the meetings for subsequent editing and distribution by the Study Chair and DCC Director;
- Arranging meetings of the EC, STC, QAC, and FIG, making technical, travel, and food arrangements, assisting chairpersons of these committees, and preparing and distributing minutes to members of the appropriate committee;
- Arranging scheduled telephone and conference calls;
- Maintaining office supplies for the Chair's Office; and
- Typing and distributing study correspondence, relevant reports, and/or manuscripts.

In addition, s/he will assist the Study Chair in budgeting and accounting activities of the Study Chair's office. These activities will include:

- Coordinating execution of the CRADAs among the University of Alabama, military Clinical Centers, and the Johns Hopkins University;
- Payments and tracking of expenditures for personnel, equipment, supplies, etc., associated with the Study Chair's office;
- Payment or reimbursement of travel expenses for committee and group meetings, training meetings, site visits, etc.
- Payment for all meeting expenses (e.g., food and audiovisual equipment);
- Purchase and accounting of all SGs for Clinical Centers; and
- Day-to-day financial operations of the Study Chair's office.

## **20.4 Preparations for Study Meetings**

The Chair's Office prepares and arranges for meetings of the EC, STC, QAC, and FIG. These preparations shall include setting an agenda, selecting a location, and managing details for accommodation. EC meetings are held on a monthly basis via conference telephone call. Face-to-face meetings of the STC and QAC are scheduled to coincide with meetings of the FIG, which are held annually. The STC meets by conference call at least monthly between face-to-face meetings.

## **20.5 Preparation of Recruitment Materials**

The Study Chair's Office will work closely with the individual Clinical Centers to market the TRTT and enhance participant recruitment. Relevant marketing materials will be prepared by the Study Chair's Office in conjunction with local Clinical Centers. National presentations with Military Clinical Center Directors will be coordinated to promote the TRTT at annual Tri-Care meetings of military audiologists and physicians who may be potential sources of participant referrals. Initially the Study Chair will describe the purposes and objectives of the study at training and orientation meetings for participating Clinical Center members in the TRTT. Topics included will be randomization, treatment options, length of follow-up, outcome measures, and local recruitment issues specific to participating Clinical Centers. Topics for subsequent years include baseline features of enrolled Study Participants, which will be monitored closely with each Clinical Center to ensure fulfillment of target enrollment of minority and women participants.

## **20.6 Preparation of Training Videotape**

Standardization of the treatment sessions including DC, SC, and SG fitting sessions, will be accomplished in part through viewing study video tapes prepared by the Training/Protocol Monitors. These tapes will review the steps to be performed in the counseling and ST fitting sessions, as well as follow-up counseling sessions. Use of these tapes should enhance standardization across Clinical Centers and minimize confounding problems or extraneous matters being introduced into a given session. Copies of videotapes will be distributed to each of the Clinical Centers.

## **20.7 Publication and Presentation of Study Findings**

The Study Chair's Office will work with the DCC and TRTT investigators to prepare publications and scientific presentations to report the findings of this study and the TRTT design.

---

### **21.1 Introduction**

General Hearing Instruments, Inc.(GHI), located in New Orleans, Louisiana, will provide the sound therapy devices used for sound therapy in the Tinnitus Retraining Therapy Trial (TRTT). Sound therapy (ST) is an integral component of Tinnitus Retraining Therapy (TRT) and aims to facilitate the habituation process by decreasing the contrast between tinnitus-related and background neuronal activity. GHI manufactures the sound generator (SG) that will be used to provide sound therapy in the TRTT. This instrument is the digital equivalent of the Tranquil model SG. The digital devices will be implemented with added features including data-logging capability to enable the Study Audiologist to monitor the Study Participant's use of the SGs and ST protocol compliance.

### **21.2 Organization**

[name], President of GHI, will oversee manufacturing and quality control of the devices together with [name], Director of Product Development. They will ensure the acoustic output characteristics of all devices used in the TRTT. Generally, Clinical Centers will not contact GHI directly, but will contact the TRTT Data Coordinating Center (DCC) if any problems arise with respect to supply or distribution of original or replacement devices. Direct contact with GHI may be necessary when questions or problems arise which are related to the data-logging capabilities of devices.

### **21.3 Responsibilities**

GHI will work in coordination with the Study Chair and the DCC to facilitate custom device production and timely delivery of the SG devices for each Study Participant assigned to ST at all

---

six (6) Clinical Centers. GHI also will provide the necessary hardware and software to download and analyze each Study Participant's ST usage pattern and sound exposure history. The usage pattern will be used by the Study Audiologist at follow-up visits to assess ST compliance and for counseling of non-compliant participants.

### **21.3.1 Manufacture of Devices**

GHI will manufacture all devices used in the TRTT. Approximately half the manufactured devices will be configured as conventional SGs and the remainder will be configured as placebo SGs. Although it is expected that about 76 participants will be randomized to each type of device, additional devices of each type (conventional and placebo) will be required when a device needs to be replaced because of loss or damage. Devices will be manufactured and packaged as pairs (one for the left ear and one for the right ear) and lost or damaged devices will be replaced as pairs. Each pair of devices will be identified using sequential serial numbers and packaged in a kit which itself has a kit ID. The serial numbers for the devices for the right and left ear will be identical except that the last digit will be "R" or "L", respectively.

### **21.3.2 Randomization of Devices**

GHI will provide the TRTT DCC with a block of at least 600 serial numbers (300 pairs) that will be used to identify and represent the full set of instruments for the study, including those to be used as randomly assigned devices as well as replacement devices. The DCC will randomly designate which sets of serial numbers will be used for the conventional devices and which for the placebo devices. The DCC will also generate randomization assignments by kit ID, and matching conventional devices with assignment to full TRT and placebo devices with assignment to partial TRT. Because randomization is stratified by Clinical Center, randomization will also determine which devices will be sent to which Clinical Center.

[figure not shown]
### **21.3.3 Distribution of Devices**

At the beginning of the study, the TRTT used behind-the-ear devices and the DCC was responsible for distribution of devices to Clinical Centers. GHI sent a sufficient number of pairs of SGs to the DCC to supply all 6 Clinical Centers with the first 6 randomized treatment assignments. Each SG pair is housed in a single container.

The DCC placed each container within a box having a kit ID. Each box had a sheet of paper noting the treatment assignment, either TRT (Directive Counseling and Sound Therapy) or Standard of Care (SC). Boxes for Study Participants assigned to TRT also contained the pair of SGs assigned to that Study Participant. The DCC affixed a tear-off label to each kit. The label included the kit ID and a tear-off portion to be affixed to the Sound Generator Issue Form for

Study Participants assigned to TRT or to the Standard of Care Checklist for Study Participants assigned to SC.

Figure 1. Sample tear off label

In order to maintain a constant stock of SG pairs at each Clinical Center, after a series of randomized treatment assignments involving an SG, the DCC sent an email to GHI requesting replenishment of the stock at the DCC. GHI sent the requisite SGs within two business days.

Part-way through the trial, it became obvious that for some Study Participants, the behind-the-ear devices failed at an unacceptable rate and the decision was made to preferentially use non-occluding in-the-ear devices from that point forward. The DCC will continue to send kits with tear-off labels to the Clinical Centers, but instead of including a box containing the sound generators, the kit will include a sheet of paper noting the treatment assignment, either TRT or SC, and a Sound Generator Order Form. The Sound Generator Order form will include the serial number of the assigned device and a place for the Clinical Center to indicate the preferred color for the device. When the impressions for in-the-ear devices have been obtained and are ready to be shipped to GHI, the Sound Generator Order Form is completed and faxed to both GHI and the DCC. This action notifies GHI about the requisite sound generators to be manufactured. A copy of the Sound Generator Order Form is included in the Study Participant's file, and the original placed in the box with the impressions to be shipped to GHI.

When the manufacture of the devices has been completed, GHI will notify the DCC by email on the day the sound generators are shipped to the Clinical Center.

At the end of the trial, if TRT proves to be successful, any unused devices will be offered to Study Participants assigned to SC.

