#### **22.2.4 Randomization**

During the study database design, tables of randomized treatment assignments will be created. These tamper-proof tables will contain already generated random assignments that will be allocated at the time of randomization. These tables will contain randomly permuted blocked allocations, stratified by Clinical Center, and will be accessible online or by DCC staff if and when a Clinical Center telephones for a randomized treatment assignment.

A standard report will be generated at randomization, which will be available online immediately following randomization. It will designate the kit ID assigned to the Study Participant. The actual assignment, TRT (Directive Counseling (DC) and sound generator (SG)), or the standard of care (SC), will be contained within the kit itself. If assigned to TRT, the kit will also include the pair of Sound Generators to be used for Study Participants assigned to TRT.

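### Each centre's coming assignments sit on site in kits that name the arm and, for behind-the-ear devices, differ in content, so TRT versus SC can be partly predicted

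*Combined protocol and SAP*

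**What the plan says.** Section 22.2.4 has the online report give only a kit ID at randomization. The arm itself "will be contained within the kit itself", and "If assigned to TRT, the kit will also include the pair of Sound Generators". Section 21.3.3 describes the supply. The manufacturer sent the DCC enough pairs to "supply all 6 Clinical Centers with the first 6 randomized treatment assignments", and the DCC boxed each assignment with a sheet stating TRT or SC. TRT boxes also held the devices: "Boxes for Study Participants assigned to TRT also contained the pair of SGs assigned to that Study Participant". A standing stock at the centres was intended. Section 14.9.3 has centres log receipt of both SC kits and device kits.

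Part-way through the trial, in-the-ear devices became the preferred type. From then on, "The DCC will continue to send kits with tear-off labels to the Clinical Centers", now with the assignment sheet and a Sound Generator Order Form in place of the devices. Behind-the-ear kits are not excluded: Section 12.2.1 still provides for them.

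There are safeguards. The assignment tables are pre-generated, held centrally and described as tamper-proof (22.2.4). The kit ID is disclosed only at randomization (12.2.1, 22.2.4). Blocks are of random size, stratified by centre (23.1.1). The Eligibility Screening Form, the TQ and the Eligibility Checklist must be entered before an assignment is requested (18.5.1). Section 23.1.1 refers to Chapter 5 for the logistics of randomization; that chapter is not in the part reviewed.

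**The concern.** Allocation concealment depends on nobody at the centre being able to tell what the next participant will receive. Here the answer is already in the building, in boxes whose contents differ by arm during behind-the-ear use. The tamper-proof protection in 22.2.4 covers the database tables, not the boxes.

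The exposed contrast is TRT versus SC. It is not masked: 23.1.1 promises blinding only for conventional versus placebo devices. It contains the primary comparison (Group 1 versus Group 3) and the directive-counseling comparison (Group 2 versus Group 3). The primary outcome is a questionnaire completed by the participant. If staff acted on a forecast of the arm when timing an enrolment, the groups could differ systematically at entry. Intention-to-treat analysis does not remove such a difference, a larger sample does not remove it, and covariate adjustment deals only with what was measured.

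**Working it through.** The plan states no figure for predictability, so there is none to reproduce. The sample size of 228 is used only for the allocation ratio and is not in dispute.

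**Inputs from the documents**
- 76 participants in each of three groups (23.2.3). Groups 1 and 2 are both TRT kits, so TRT:SC = (76 + 76):76 = 2:1.
- Initial supply of six assignments, read as six per centre (21.3.3).

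**Assumptions, not in the documents**
- The six kits are exactly 4 TRT and 2 SC. Random block sizes do not guarantee this.
- Staff know the contents of the stock.
- The stock is used up before resupply.

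**Case A: contents unknown.** Always guessing TRT is right 4/6 = 66.7% of the time.

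**Case B: contents known, issue order unknown.** There are C(6,2) = 15 equally likely orders. Staff guess whichever arm is in the majority among the remaining kits; a tie counts as one half. The chance of a correct guess at each draw is:
- Draw 1: 4/6 = 0.667
- Draw 2: (2/3)(3/5) + (1/3)(4/5) = 0.667
- Draw 3: (1/15)(1) + (8/15)(3/4) + (6/15)(1/2) = 0.667
- Draw 4: (3/15)(1) + (9/15)(2/3) + (3/15)(2/3) = 0.733
- Draw 5: (7/15)(1) + (8/15)(1/2) = 0.733
- Draw 6: 1

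The mean is (3 × 0.6667 + 2 × 0.7333 + 1)/6 = 4.4667/6 = **74.4%**.

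An assignment is certain in advance when only one arm remains. The expected number of TRT kits after the last SC kit is 4/(2+1) = 1.333. The expected number of SC kits after the last TRT kit is 2/(4+1) = 0.400. The share that is certain is (1.333 + 0.400)/6 = **28.9%**.

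**Case C: contents known and issue order known** (for example, shelf order). Prediction is 100%.

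**Sensitivity of Case B to stock size, at 2:1**

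| Stock | Correct guesses | Certain in advance |
|---|---|---|
| 3 | 77.8% | 44.4% |
| 6 | 74.4% | 28.9% |
| 9 | 72.8% | 21.4% |
| 12 | 71.7% | 17.0% |

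**In-the-ear kits.** No devices are packed, so weight and feel tell staff little. Section 21.3.3, read literally, puts an order form in the kit without limiting it to TRT. Section 12.2.1 and Appendix A of Chapter 12 tie the form to TRT assignments. Whether SC kits hold a form is therefore unsettled. Either way the contents are paper, and the arm is learned mainly by opening the kit.

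**The case against.** The strongest counter-argument is that the plan does control what matters most. The kit ID comes from central tables and is released only at randomization, so knowing what is in a box does not show which box comes next. Chapter 5 may specify sealing, matched boxes and an unpredictable issue order, and text in a part not seen cannot be called missing. The device-versus-paper difference is described mostly in the past tense. There are also checks on deferral: everyone screened is registered whatever the result (14.3.1), pending status goes to the DCC with a date (14.4.2) and is tracked (22.2.3), and the Kit Log is reviewed at site visits (14.9.3).

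Much of this stands. A reader might infer that staff can know the arm of every next participant; the documents do not support that, because they do not say that kits are issued in a known order. A reader might also infer that the coordinator who verifies eligibility handles the kits; Sections 14.9.3 and 18.4.2.2 do not say who receives or logs them. The 29% depends on the stock being run down, whereas 21.3.3 speaks of a constant stock.

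What remains is that central release hides which kit is next but not what is left on the shelf. Sealing alone would not make a device kit feel like a paper-only kit. Random block size does not help, because the information comes from the physical stock. Records of screening and pending status help to detect deferral afterwards; they do not conceal the assignment. Nor is behind-the-ear use purely historical, since 12.2.1 and 22.2.4 still describe kits with devices inside.

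**Conclusion.** The concern holds as a partial weakness in allocation concealment for TRT versus SC. Assignments are on site in advance, the arm is written inside each kit, and behind-the-ear kits differ in content by arm. The pages available describe no physical concealment of the boxes.

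Under the stated assumptions for a stock of six, the gain is just under 8 percentage points in correct guesses (74.4% against 66.7%), with 28.9% of assignments certain. Full predictability needs a known issue order or a stock reduced to one arm. For in-the-ear kits the exposure is smaller. The conventional/placebo mask is unaffected. Nothing in the documents allows the effect to be turned into TQ points, and nothing shows that any assignment was in fact foreseen. The conclusion could soften further if Chapter 5 specifies matched, sealed kits and an unpredictable issue order.

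**What to change.** In 21.3.3 and 22.2.4, remove the assignment sheet from pre-shipped kits. Have the existing online randomization report, or the DCC when a centre telephones, release TRT or SC only after the Eligibility Screening Form, the TQ and the Eligibility Checklist have been entered, as 18.5.1 already requires. Limit that view to the coordinator and the treating audiologist, using the role-based access in 22.5, so that the second audiologist stays blinded as 17.2.1 requires.

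For TRT, release at the same moment either a kit ID from a device-only stock or, for in-the-ear devices, the order form with its serial number. The conventional/placebo mask then stays in the serial number, SC needs no kit, and the stock on the shelf says nothing about the next arm.

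Check Chapter 5 for sealing, matching and issue order. If the kits are kept as they are, state that they are sealed, opaque, matched in weight and size across arms, and issued in unpredictable order. Reconcile 21.3.3 with 12.2.1 and Appendix A of Chapter 12 on whether SC kits contain an order form.

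The cost is a small change to the report and its access rights, a new source for the label that now goes from the kit to the Standard of Care Checklist, and one policy memorandum. No visits or staff are added.
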